6.3. Exclusion Criteria

The presence of any of the following will exclude a subject from enrollment:

1. Other than disease under study, any clinically significant (as determined by the Sponsor Investigator) cardiac, endocrinologic, pulmonary, neurologic, psychiatric, hepatic, renal, hematologic, immunologic disease, or other major disease that is currently uncontrolled.
2. Any condition which would place the subject at unacceptable risk if he/she were to participate in the study.
3. Prior history of suicide attempt at any time in the subject's life time prior to screening or baseline, or major psychiatric illness requiring hospitalization within the last 3 years.
4. Pregnant or breast feeding.
5. Active substance abuse or a history of substance abuse within 6 months prior to Screening.
6. Malignancy or history of malignancy, except for:
 - a. treated [ie, cured] basal cell or squamous cell in situ skin carcinomas;
 - b. treated [ie, cured] cervical intraepithelial neoplasia (CIN) or carcinoma in situ of cervix with no evidence of recurrence within the previous 5 years.
7. Use of any investigational drug within 4 weeks prior to baseline, or 5 pharmacokinetic/pharmacodynamic half-lives, if known (whichever is longer).
8. Prior treatment with apremilast.
9. Concomitant use of drugs that treat psoriasis including but not limited to methotrexate, acitretin, cyclosporine within 4 weeks of baseline.
10. Adalimumab, etanercept, efalizumab, infliximab, or certolizumab pegol within 12 weeks prior to baseline.
11. Alefacept, briakinumab, ixekizumab, brodalumab or ustekinumab within 24 weeks prior to baseline.
12. Use of phototherapy within 4 weeks prior to baseline (i.e., UVB, PUVA)
13. Plaque-type psoriasis with BSA<10%
14. Psoriasis predominantly involving the face or folds (groin or axilla)
15. Psoriasis only of the palms/soles, pustular or other forms of psoriasis
16. Concurrent skin or systemic infection
17. History of intolerance to topical steroids or apremilast.
18. Topical therapy within 2 weeks of baseline (including but not limited to topical corticosteroids, topical retinoids or vitamin D analog preparations, tacrolimus, pimecrolimus, or anthralin/dithranol). Exceptions: Clobetasol Spray 0.05%.

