2. STUDY OBJECTIVES

2.1. Primary Objective

Proportion of patients achieving PASI (Psoriasis area and Severity Index) 75 at Week 16 from baseline.

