3. OVERALL STUDY DESIGN

Open label, pilot trial with 20 patients with psoriasis vulgaris involving the body with or without scalp plaques

The study is designed as a 16-week study and consists of 8 visits as described in the table of events.

Screening

To reduce risk of gastrointestinal symptoms, titrate to recommended dose of 30 mg BID according to the following schedule:

- Day 1: 10 mg in morning
- Day 2: 10 mg in morning and 10 mg in evening
- Day 3: 10 mg in morning and 20 mg in evening
- Day 4: 20 mg in morning and 20 mg in evening
- Day 5: 20 mg in morning and 30 mg in evening
- Day 6 and thereafter: 30 mg twice daily

Weeks 0-2

Patients will receive apremilast 30 mg BID and clobetasol spray 0.05% to affected plaques BID for 2 weeks. The first week of IP dosing will consist of apremilast dose-titration card.

Weeks 2-4

Patients will receive apremilast 30 mg BID and clobetasol spray 0.05% to affected plaques once daily for 2 weeks

Weeks 4-6

Patients will receive apremilast 30 mg BID and clobetasol spray 0.05% to affected plaques every other day for 2 weeks, then stop clobetasol spray 0.05%

Weeks 6-16

Patients will continue to receive apremilast 30 mg BID

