8.2. Prohibited Concomitant Medications and Procedures

The following psoriasis medications cannot be administered for the duration of the study:

- Topical corticosteroids, except for study drug, Clobetasol Spray 0.05%
- Phototherapy
- Oral systemic drugs for psoriasis including: methotrexate, cyclosporine, acitretin
- Biologics treatments for psoriasis: adalimumab, etanercept, infliximab, ustekinumab, secukinumab, ixekizumab, brodalumab

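### Secukinumab is the only biologic barred on study that has no biologic washout before baseline; at most a general 4-week rule reaches it

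*Combined protocol and SAP*

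**What the plan says.** Section 8.2 sets the on-study ban. It opens with "The following psoriasis medications cannot be administered for the duration of the study" and lists, among others, "Biologics treatments for psoriasis: adalimumab, etanercept, infliximab, ustekinumab, secukinumab, ixekizumab, brodalumab". The ban covers use during the study and sets no interval before baseline.

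Intervals before baseline are set in Section 6.3:

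- Exclusion 10: "Adalimumab, etanercept, efalizumab, infliximab, or certolizumab pegol within 12 weeks prior to baseline".
- Exclusion 11: "Alefacept, briakinumab, ixekizumab, brodalumab or ustekinumab within 24 weeks prior to baseline".
- Exclusion 9, a general rule: "Concomitant use of drugs that treat psoriasis including but not limited to methotrexate, acitretin, cyclosporine within 4 weeks of baseline".
- Exclusion 7 covers earlier investigational drugs only (4 weeks or five half-lives, whichever is longer).

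Exclusions 10 and 11 are closed lists. Only exclusion 9 is open-ended.

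The primary objective (Section 2.1) is "Proportion of patients achieving PASI (Psoriasis area and Severity Index) 75 at Week 16 from baseline". The design (Section 3) is "Open label, pilot trial with 20 patients with psoriasis vulgaris involving the body with or without scalp plaques", and no control group is described.

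**The concern.** The plan treats earlier biologic use as something that must be cleared before baseline, and it asks for 12 or 24 weeks. Secukinumab is recognised as a psoriasis biologic in Section 8.2 but has no such requirement. A site following the text could enrol a patient a little over 4 weeks after the last dose. If exclusion 9 is read narrowly, it could do so sooner.

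PASI 75 is a change from baseline, so residual drug effect can enter at both ends: through the score that the 75% reduction is measured from, and through the Week 16 score. A concurrent control group with similar prior treatment would show how much change came from the earlier drug. This trial has none, and Section 9.5 plans descriptive summaries with no adjustment for prior biologic use. Any carry-over would therefore be counted for or against the study regimen and could not be separated from it.

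**Working it through.** **1. Match the seven biologics in Section 8.2 to Section 6.3.**

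| Biologic barred on study (8.2) | Biologic washout (6.3) |
|---|---|
| Adalimumab | 12 weeks (exclusion 10) |
| Etanercept | 12 weeks (exclusion 10) |
| Infliximab | 12 weeks (exclusion 10) |
| Ustekinumab | 24 weeks (exclusion 11) |
| Ixekizumab | 24 weeks (exclusion 11) |
| Brodalumab | 24 weeks (exclusion 11) |
| Secukinumab | none |

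Six of seven are covered, and secukinumab alone is not.

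**2. What reaches it instead.** Exclusion 7 applies only if the earlier drug was investigational. That leaves exclusion 9, at 4 weeks. This is the most protective reading available: the criterion speaks of concomitant use, and its three named examples (methotrexate, acitretin, cyclosporine) are the drugs that Section 8.2 lists as oral systemics, separately from biologics. A reader who takes exclusion 9 not to cover biologics is left with no numeric washout for marketed secukinumab.

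**3. Size of the gap, taking the 4 weeks.**

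- Against the shorter biologic window: 12 − 4 = 8 weeks.
- Against the longer one: 24 − 4 = 20 weeks.

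**4. Time since last dose at the endpoint.** For entry at just over 4 weeks, Week 16 falls about 4 + 16 = 20 weeks after the last dose. By the plan's 24-week standard, both the baseline and the Week 16 score fall inside the window. By its 12-week standard, only the baseline score does.

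**5. Direction.** Let B and W be the baseline and Week 16 PASI without residual effect, and let r0 and r16 be the points that residual effect removes at each visit. If the effect is additive, a patient responds when

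W − r16 ≤ 0.25 × (B − r0), that is, W ≤ 0.25 × B + (r16 − 0.25 × r0).

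Carry-over makes response easier if r16 exceeds 0.25 × r0 and harder if it is smaller. A baseline lowered by drug that then wears off works against response; effect that persists to Week 16 works for it. If residual effect acts proportionally instead, a waning effect only makes response harder. The documents give no half-life or duration of effect for secukinumab, so the sign cannot be fixed.

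**6. Weight of one patient.** 1/20 = 5 percentage points, reached only if carry-over changes that patient's responder status. Against the roughly 30% response on apremilast alone cited in Section 1, this is the difference between 6/20 = 30% and 7/20 = 35%. For scale, the exact 95% interval for 6/20 is 11.9% to 54.3%, so one patient's shift is small beside sampling error, though it is a bias and not noise.

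**The case against.** The strongest case for leaving the text alone is that the consequence is remote. Entry requires at least 10% BSA (inclusion 3, exclusion 13), so a patient still well controlled by an earlier biologic would often not qualify. The trial is a 20-patient pilot with descriptive reporting, no test and no decision threshold. One-in-twenty arithmetic applies to any single-patient problem in a trial of this size. All of this stands, and it limits the size of the point. It does not close the gap: the entry rule sets a floor on BSA and none on PASI, so a partly suppressed patient can still enter.

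A reader might infer that secukinumab belongs with the 24-week agents because Section 8.2 prints it between ustekinumab and ixekizumab, and so put the gap at 20 weeks. The order of names in a list says nothing about washout length, and nothing in the documents favours 24 weeks over 12. Only the range of 8 to 20 weeks is supported.

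A reader might also infer a matching fault in the other direction, because certolizumab pegol has a washout but is missing from Section 8.2. So are efalizumab, alefacept and briakinumab; adding certolizumab alone would leave the lists three agents apart. Little turns on this, because Section 8.1 already allows only drugs that are not expected to affect the assessments, and a psoriasis biologic started on study would fail that test.

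**Conclusion.** The omission is plain on the text: one of the seven biologics barred on study has no biologic washout. The fallback is 4 weeks at best, which is 8 to 20 weeks shorter than the plan requires for the other six.

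The effect on the result is conditional. It needs a patient who used secukinumab recently, still meets the BSA rule, and has enough residual effect to change PASI 75 status. Each such patient is worth up to 5 percentage points, in a direction that the documents do not determine. The number of such patients is unknown and may be zero. That carry-over is possible at all is inferred from the windows the plan sets for other biologics, not from any stated property of secukinumab. It would be too strong to say that the primary result will be biased, or by how much. This is a modest eligibility inconsistency that is cheap to close before enrolment and hard to repair afterwards.

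**What to change.** Reconcile Section 6.3 with Section 8.2 by naming secukinumab explicitly in a biologic washout criterion, so that every biologic barred on study has a stated interval before baseline. The length of the window is a clinical decision for the sponsor; it should be written down and not left to exclusion 9 by default.

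The cost is one entry in one list. It needs no new procedure and no change to the sample size or analysis. A rare recently treated patient may be excluded or have to wait. No change to Section 8.2 is needed for this point.

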7. DESCRIPTION OF STUDY TREATMENTS

7.1.1. Treatment Administration and Schedule

Otezla is given as an initial 5-day titration schedule starting at 10 mg on day 1, 10 mg BID on day 2, 10 mg qam and 20 mg qhs day 3, 20 mg BID day 4, 20 mg qam and 30 mg qhs day 5. At and after day 6 the dose is 30mg BID.

Clobetasol 0.05% spray is applied to plaques on body and scalp, but not face and folds, BID for 2 weeks. Then qd for 2 weeks then qod for 2 weeks.

7.1.2. Packaging and Labeling

Tablets

The label(s) for Otezla will include drug name, dosage form and strength (where applicable), amount of Otezla per container, lot number, expiry date (where applicable), dosing instructions, storage conditions, and required caution statements and/or regulatory statements as applicable. Additional information may be included on the label as applicable per local regulations.

All apremilast will be supplied by Celgene.

Clobetasol 0.05% spray is supplied in a 120ml bottle with spray pump.

7.1.3. Product Accountability and Disposal

The Sponsor Investigator, or designee, is responsible for taking an inventory of each shipment of Otezla received, and comparing it with the accompanying Otezla shipping order/packing list. The Sponsor Investigator, or designee, will verify the accuracy of the information on the form, sign and date it, retain a copy in the study file, and return a copy to Celgene.

The Sponsor Investigator, or designee, is responsible for taking an inventory of each shipment of clobetasol 0.05% spray received. Disposal and /or destruction will be performed by the Sponsor or designee.

Investigational product will be stored per the storage conditions identified on drug label. At the study site, all Otezla and clobetasol 0.05% spray bottles will be stored in a locked, safe area to prevent unauthorized access.

Celgene will instruct the Sponsor Investigator on the return, disposal and/or destruction of Otezla if applicable.

7.1.4. Investigational Product Compliance

Study personnel will review the instructions printed on the package with the study subjects prior to dispensing Otezla and clobetasol spray. The subjects will be instructed to return the Otezla containers and clobetasol spray bottles, including any unused medication, to the study site at each visit for tablet counts and reconciliation. Subjects will be asked whether they have taken their Otezla and clobetasol spray as instructed at each study visit. Any problems with compliance will be reviewed with the subject.

8. CONCOMITANT MEDICATIONS AND PROCEDURES

8.1. Permitted Concomitant Medications and Procedures

Subjects may take any medication that is not restricted by the protocol and would not be expected to interfere with the conduct of the study or affect assessments. Chronic medication should be dosed on a stable regimen.

All medications (prescription and non-prescription), treatments and therapies taken by the subject from screening throughout their entire participation in the study, including those initiated prior to the start of the study, must be recorded on the subject's source document and on the appropriate page of the CRF. The dose, unit, frequency, route, indication, the date the medication was started and the date the medication was stopped (if not ongoing) must be recorded. The recording of any permitted topical medications taken for psoriasis should also include the area of the body to which they are applied.

The following topical therapies will be permitted:

- Unmedicated skin moisturizer (e.g., Eucerin or Cetaphil) permitted for body lesions only

8.2. Prohibited Concomitant Medications and Procedures

The following psoriasis medications cannot be administered for the duration of the study:

- Topical corticosteroids, except for study drug, Clobetasol Spray 0.05%
- Phototherapy
- Oral systemic drugs for psoriasis including: methotrexate, cyclosporine, acitretin
- Biologics treatments for psoriasis: adalimumab, etanercept, infliximab, ustekinumab, secukinumab, ixekizumab, brodalumab

8.3. Required Concomitant Medications and Procedures

Clobetasol spray 0.05% spray is applied to plaques on body and scalp, but not face and folds, BID for 2 weeks. Then qd for 2 weeks then qod for 2 weeks

9. STATISTICAL ANALYSES

9.1. Overview

We will report the number of patients who achieve a clinical response to the primary and secondary objectives as outlined.

9.2. Sample Size

The proposed sample size is based on clinical setting, practice size, number of patients able to be included within the 1-year time period. Approximately 20 patients will be enrolled into the study.

9.3. Background and Demographic Characteristics

Patients' age, weight, height and other continuous demographic and baseline characteristics will be summarized using descriptive statistics (n, mean, standard deviation, median, minimum, and maximum), while gender, race and other categorical variables will be summarized. Medical history data will be summarized using frequency tabulations.

9.4. Subject Disposition

Patient disposition (analysis population allocation, entered, completed, discontinued, along with primary reason for discontinuation) will be summarized using frequency and percent by phase.

9.5. Efficacy Evaluation

Efficacy analysis will be based on all patients enrolled as specified in the protocol. Responders are those who achieve at least a PASI-75 at Week 16; non-responders are defined as those who do not achieve a PASI-75 at Week 16 and/or those who have missing data at any time point during the study.

The proportion of patients who achieve at least a PASI-75 at Week 16 (responders) reference to the baseline, proportion of patients with scalp psoriasis with improvement of ScPGA scores to 0 and 1 at Week 16, change from baseline in Pruritus VAS at Week 16, mean percent change from baseline in BSA x PGA at Week 16 will be summarized using descriptive summary statistics for continuous variables, while frequency and percentages will be provided for discrete variables

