5. PROCEDURES

The following procedures will be conducted as outlined in the Table of Events.

Informed Consent

An Informed Consent Document will be signed by the subject before any study-related assessments are performed.

Contraception Education

The risks to a fetus or to a nursing child from apremilast are not known at this time. Results of the animal and in vitro studies can be found in the IB.

All females of childbearing potential (FCBP) must use one of the approved contraceptive options as described in section 4.2 while on investigational product and for at least 28 days after administration of the last dose of the investigational product.

When a female subject of childbearing potential's contraceptive measures or ability to become pregnant changes at the time of study entry or at any time during the study, the Sponsor Investigator will educate the subject regarding options and correct and consistent use of effective contraceptive methods in order to successfully prevent pregnancy.

Inclusion/Exclusion Criteria

Subjects must meet all inclusion criteria and must not have any of the conditions specified in the exclusion criteria to qualify for participation in the study. The subject's source documents must support his/her qualifications for the study (e.g., if a female subject does not require pregnancy testing and birth control because of a hysterectomy, the date of the hysterectomy must be included in the medical history).

Medical and Disease History

Relevant medical history should be recorded, including smoking and alcohol history, as well as previous relevant surgeries. Disease history includes history of psoriasis, psoriatic arthritis and chronic infections.

Prior/Concurrent Medications and Therapies

All medications and therapies being taken/used by the subject at the time of consent or at any time during the study will be recorded. Other key medications and therapies will be recorded.

Safety Assessments

The following assessments will be conducted as outlined in the Table of Events.

Psoriasis Flare and Rebound Assessments

Psoriasis flare is an AE (and will be recorded as an AE) and represents an atypical or unusual worsening of disease during treatment. It is defined as a sudden intensification of psoriasis requiring medical intervention or a diagnosis of new generalized erythrodermic, inflammatory, or pustular psoriasis. A more typical, gradual worsening of plaque psoriasis would not be recorded as an AE.⁵

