10.3. Action Taken

The Sponsor Investigator will report the action taken with Otezla and Clobetasol spray as a result of an AE or SAE, as applicable (e.g., discontinuation of IP, as appropriate) and report if concomitant and/or additional treatments were given for the event.

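### Section 9.5 counts a complete-data patient with PASI-75 at Week 16 as a responder even after prohibited psoriasis therapy or clobetasol used beyond the Week-6 stop

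*Combined protocol and SAP*

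**What the plan says.** Section 9.5 analyses all enrolled patients and sorts them on two facts. "Responders are those who achieve at least a PASI-75 at Week 16"; non-responders are "those who do not achieve a PASI-75 at Week 16 and/or those who have missing data at any time point". Concomitant therapy and adherence to the clobetasol taper do not enter the definition.

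The treatment restrictions are elsewhere:

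- Section 3 and the footnote to the Table of Events (section 4) end clobetasol at Week 6, after two weeks each of twice-daily, daily and alternate-day use.
- Section 8.2 opens with "The following psoriasis medications cannot be administered for the duration of the study" and lists phototherapy, oral systemics, biologics and one topical class: "Topical corticosteroids, except for study drug, Clobetasol Spray 0.05"%. That entry carries no Week-6 limit of its own.
- Section 8.1 allows only medication not expected to affect assessments. The one topical it names is unmedicated moisturizer, for body lesions.
- Section 7.1.4 has compliance problems discussed with the patient.
- Section 11 lists protocol violation, non-compliance and lack of efficacy as sufficient grounds for stopping product, study participation or both. It does not make stopping mandatory.

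None of these sections states a consequence for responder status.

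**The concern.** Sections 1 and 3.1 give the rationale: clobetasol induces a response and apremilast maintains it. Week 16 is when maintenance is judged, ten weeks after clobetasol should have stopped. A PASI-75 reached after phototherapy, another steroid or continued clobetasol does not show maintenance on apremilast. With a single arm, there is no control group to put it in context.

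The case is foreseeable even though no rescue pathway is planned. The protocol summary gives the risk of rebound after abrupt withdrawal as the reason for the taper. Flare is defined partly as "a sudden intensification of psoriasis requiring medical intervention" (section 5). Under section 10.3 the investigator is to "report if concomitant and/or additional treatments were given for the event". The protocol does not say what that intervention may be, or how the endpoint treats a patient who receives it.

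At stake is the meaning of the primary proportion for these patients. If the rule is not set in advance, an unblinded sponsor-investigator would have to decide such cases after seeing the outcome.

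**Working it through.** **Step 1: the text.** Take a patient who uses a barred therapy, or clobetasol after Week 6, and follow that patient through the plan.

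- Withdrawn from the study before Week 16: later visits are missing, so 9.5 makes the patient a non-responder. There is no gap here.
- Kept in the study, or taken off product only, with every visit complete and PASI-75 at Week 16: both conditions in 9.5 are met, so the patient is a responder.
- Kept in the study, with PASI-75 not reached: non-responder under any rule.

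The gap is the second case only. Two phrases might seem to close it. Section 9.5 refers to patients enrolled as the protocol specifies, and section 9.4 mentions allocation to analysis populations. No compliant-only population or exclusion rule is defined, so the natural reading is all enrolled patients.

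**Step 2: timing.** Clobetasol stops at Week 6 and the endpoint is at Week 16: 16 − 6 = 10 weeks. PASI is scheduled in that interval at Weeks 8, 12 and 16.

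**Step 3: size.** The plan has no calculation to reproduce, because section 9.2 sets about 20 patients on feasibility. Let g be the Week-16 responders with complete data and no such use, and k those with complete data who reach PASI-75 after such use.

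- Written rule: (g + k)/20
- Rule counting such use as non-response: g/20
- Difference: k/20

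| k | Difference |
|---|---|
| 0 | 0 points |
| 1 | 1/20 = 5 points |
| 2 | 2/20 = 10 points |

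The documents give no basis for k, so these values are assumptions. If j of the k patients would have reached PASI-75 without the extra therapy, the distortion is (k − j)/20, which is smaller.

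**Step 4: scale against precision.** As an illustration, assume g = 6, to match the figure of about 30% for apremilast alone in sections 1 and 3.1. Intervals are exact (Clopper-Pearson) 95%.

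| Responders | Rate | Interval | Width |
|---|---|---|---|
| 6/20 | 30% | 11.9% to 54.3% | 42.4 points |
| 7/20 | 35% | 15.4% to 59.2% | 43.8 points |

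One such patient moves the estimate by 5 points, about an eighth of the interval width (5/42.4 = 0.12).

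**The case against.** The strongest reply is that the omission has little practical reach. For it to matter, a patient must use barred therapy, be kept in the study, miss no data, reach PASI-75, and not have reached it otherwise. Sections 8.1 and 8.2 already restrict the alternatives, section 11 permits removal, and removal from the study leads to failure through missing data. The trial is an open-label pilot reported descriptively, so no test or success threshold depends on the result. All of this stands, and it is why the severity is low.

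A second reply is that using observed Week-16 PASI whatever else was taken is a recognised treatment-policy approach. That is true, but 9.5 does not present it as a deliberate choice, and the maintenance rationale favours the other version as primary. The fix keeps observed PASI alongside.

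A third reply concerns the remedy. A strict cut-off at the end of the taper would fail a patient who sprayed until a slightly late Week-6 visit, and the Table of Events gives no visit windows. A literal reading of 8.1 could penalise plain moisturizer on the scalp. A rule for PASI alone would leave the secondary endpoints uncovered. These points are right, and the wording below meets them.

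A reader might also infer more than the documents support:

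- *That the reported rate is too high overall.* The same rule fails Week-16 responders who have any missing data, which pulls the other way. The net direction is unknown.
- *That the protocol plans rescue, or that a flare will be treated with barred therapy.* It has no rescue pathway, and the intervention in the flare definition need not be a prohibited one.
- *That section 8.2 permits clobetasol after Week 6.* Its entry has no time limit, but section 3 and the Table of Events require stopping.

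**Conclusion.** The gap is real and narrow. For complete-data patients who stay in the study, 9.5 as written counts PASI-75 at Week 16 as response regardless of prohibited therapy or clobetasol after the Week-6 stop. The written rate is equal to or higher than the rate under a rule that fails such patients, by k/20. With k unknown and possibly zero, the size cannot be stated beyond 5 points per patient, and one such patient is small beside the sampling uncertainty. The conclusion assumes 20 enrolled patients and the natural reading of the analysis set as everyone enrolled. It is a low-severity point, worth adopting because it aligns the endpoint with the trial's own question at almost no cost.

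**What to change.** Add to section 9.5:

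> Patients who, before the Week-16 assessment, receive a psoriasis therapy prohibited in 8.2, any other medicated topical psoriasis therapy, or clobetasol more than 7 days after the actual Week-6 visit are counted as non-responders for PASI-75 and for ScPGA 0/1. Unmedicated moisturizer at any site does not count. The number of such patients is reported, PASI-75 and ScPGA are also shown using observed values regardless of such use, and pruritus VAS and BSA x PGA are shown with and without these patients.

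Other medicated topicals are named because 8.2 lists only corticosteroids among topicals, while exclusion 18 in section 6.3 also lists "topical retinoids or vitamin D analog preparations, tacrolimus, pimecrolimus, or anthralin/dithranol". Scheduled clobetasol is not penalised, nor is over-use within the taper. The 7-day tolerance is a choice and leaves about 16 − 6 − 1 = 9 weeks before the endpoint. The missing-data rule is unchanged.

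The cost is a short paragraph, with no new visit or form. Medications are recorded under 8.1 and treatments for adverse events under 10.3. Under 7.1.4, bottles are returned and patients are asked about use.

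There are three downsides. The reported rate may be slightly lower. Some patients who would have responded anyway count as failures, and the observed-value results show how much that matters. No bottle weighing is specified and the Table of Events counts tablets only, so detection of extra clobetasol rests on medication records, returned bottles and patient report.
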